6.4 Allocation of Treatment

The results of screening assessments for each patient will be reviewed by the study PI, who will approve each patient for randomization. Upon this approval, patients will be randomized to treatment with either EACA or standard of care prophylactic platelet transfusions using a standard randomization table.

6.5 Concomitant Medications

All concomitant medications administered from the time of informed consent signature through 30 days after the end of treatment (last dose or investigator/patient decision to discontinue, whichever is later) are to be reported on the appropriate CRF for each patient.

6.5.1 Permitted Medications

All routine and appropriate supportive care (including red blood cell products) will be allowed during this study, as clinically indicated, and in accordance with the standard of care practices. Clinical judgment should be utilized in the treatment of any AE experienced by the patient. Information on all concomitant medications, administered blood products, as well as interventions occurring during the study must be recorded on the patient's CRF.

6.5.2 Prohibited Medications

Hydroxyurea and procoagulant agents including DDAVP, recombinant FVII or prothrombin complex concentrate are prohibited in patients receiving EACA.

6.5.3 Treatment Supply

6.5.3.1 Formulation, Packaging and Labeling

EACA investigational drug product is supplied as tablets. Each tablet contains 500 mg of EACA active ingredient. Tablets will be supplied as follows: 60 count in 30 cc white high density polyethylene (HDPE) bottles with induction-sealed child resistant caps. Bottle labels will bear the appropriate label text as required by governing regulatory agencies, to include product name, product strength, number of tablets, lot number, appropriate temperature range for storage and statement that drug is limited by federal law to investigational use only.

6.5.3.2 Treatment Storage, Dispensing, and Accountability

The recommended storage condition for aminocaproic acid is 25°C. The study pharmacist or designee at the site will be responsible for handling, dispensing study drug, completing associated documentary paperwork, handling dispensing log/accountability form. Each time study medication is dispensed for a patient, the following information be recorded: the patient's initials, the patient's study number, tablet strength, the number of tablets dispensed with the corresponding lot number, and the initials of the person dispensing the drug. These logs are to be maintained by the study pharmacist in the pharmacy throughout the duration of the study. The Investigator is responsible for ensuring that the patient diary card(s) and study drug provided to the patient and returned from the patient are accounted for and noted in source documentation.

6.5.3.2.1 Disposition of used supplies

All used bottles or packs of study drug must be destroyed in an appropriate manner according to the standard practice. Destruction of such supplies will be documented. During the trial and at termination, patients must return all unused study drug supplies and the return of these unused study drug supplies must be recorded. Returned supplies must not be re-dispensed. No other utilization of EACA intended for use in this study will be authorized. The Principal Investigator or his/her designee will be responsible for the appropriate handling and disposition of residual study drug.

7. Adverse Events Reporting

7.1 Adverse Events

7.1.1 Adverse Event Definition

An AE is any untoward medical occurrence in a patient or clinical investigation subject administered a pharmaceutical product and which does not necessarily have to have a causal relationship with this treatment. An AE can be any unfavorable and unintended sign (including an abnormal laboratory finding), symptom, or disease temporally associated with the use of a medicinal product whether or not considered related to the medicinal product. Any worsening of a preexisting condition, which is temporally associated with the use of the study drug (i.e., occurs after the first dose of study drug), is also an AE. Adverse events include:

- Abnormal test findings
- Changes in physical exam findings
- Other untoward medical events, regardless of their relationship to the study drug, such as injury, events that require surgery, accidents, or apparently unrelated illnesses, and hypersensitivity
- AEs may include signs or symptoms resulting from: drug overdose, drug withdrawal, drug abuse, drug misuse, drug interactions, drug dependency, and, in utero drug exposure

7.1.2 Abnormal Laboratory Tests

The criteria for determining whether an abnormal objective test finding should be reported as an AE are as follows:

- Test result is associated with accompanying symptoms that are considered clinically significant in the opinion of the investigator
- Test result requires additional diagnostic testing (other than merely repeating an abnormal test) or medical/surgical intervention
- Test result leads to a change in study drug dosing or discontinuation from the study, significant additional concomitant drug treatment, or other therapy
- Test result is considered to be an AE by the investigator

7.1.3 Performing Adverse Event Assessment

All observed or volunteered AEs, regardless of treatment group or suspected causal relationship to the investigational product, will be reported as described in the following sections. For all AEs, the investigator must pursue and obtain information adequate to determine the outcome of the AE and to assess whether it meets the criteria for classification as a serious AE requiring immediate notification to the appropriate regulatory agencies.

7.1.4 Reporting Period

Serious Unexpected Suspected Adverse Reactions require notification of the appropriate regulatory agencies beginning from the time the patient provides informed consent, which is obtained prior to the patient's participation in the clinical study (ie, prior to undergoing any study-related procedure and/or receiving investigational product), through and including 30 days after the last administration of the assigned study treatment or the investigator/patient decision to discontinue treatment, whichever occurs later. Any SAE occurring any time during the reporting period must be reported to the FDA within 15 days of determining reportability if a causal relationship to the investigational product is suspected. Any SAE ongoing at the end of the reporting period should be followed as described below. For all enrolled patients, AEs (serious and non-serious) should be recorded on the eCRF beginning with the signing of the informed consent form and concluding 30 days following the last dose of the assigned study treatment or the investigator/patient decision to discontinue treatment, whichever occurs later. AEs ongoing after the reporting period: Any ongoing AEs thought to be at least possibly study-drug related and all ongoing SAEs after this time should be followed at least every 4 weeks until they resolve to baseline (or CTCAE grade \leq 1), stabilize, or are considered to be chronic/irreversible.

7.1.5 Adverse Event Severity

The severity of AEs will be assessed according to the CTCAE, v.4.0. If the AE is not defined in the CTCAE, the investigator will determine the severity of the AE based on the following definitions:

- Mild (grade 1): The AE is noticeable to the patient but does not interfere with routine activity. The AE does not require discontinuing administration or reducing the dose of the study drug
- Moderate (grade 2): The AE interferes with routine activity but responds to symptomatic therapy or rest. The AE may require reducing the dose, but not discontinuing administration of the study drug
- Severe (grade 3): The AE significantly limits the patient's ability to perform routine activities despite symptomatic therapy. In addition, the AE leads to discontinuing administration or reducing the dose of the study drug
- Life-Threatening (grade 4): The AE requires discontinuing administration of the study drug. The patient is at immediate risk of death

- Death (grade 5): The patient dies as a direct result of the complication or condition induced by administration of the study drug

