6.3.3 Dose Reduction

Patients randomized to EACA 1000 mg twice a day or higher who experience grade ≥ 2 toxicity attributable to EACA, will hold the study drug until resolution of the adverse event to $<$ grade 1. EACA will then be reduced by 50%, restarted at 1000 mg daily after the resolution of the AE's to $<$ grade 1

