8.6 Safety Analysis

All patients receiving at least 1 dose of study drug will be considered evaluable for safety. Patients will be analyzed for safety according to the treatment which they received. Listings of laboratory test results will

also be generated, and descriptive statistics summarizing the changes in laboratory tests over time will be presented. Exposure to study drug over time will also be summarized. The AE incidence rates, as well as the frequency of occurrence of overall toxicity, categorized by toxicity grades (severity) will be described for each treatment arm and be compared between two arms using two-sided Chi-square test or t-test.

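### The fallback AE severity scale in section 7.1.5 builds study-drug action into grades 3 and 4 and causality into grade 5, which distorts the by-grade comparison for AEs outside CTCAE v4.0

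*Protocol*

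**What the plan says.** Section 7.1.5 makes CTCAE v4.0 the main scale and limits its own definitions to what CTCAE leaves out: "If the AE is not defined in the CTCAE, the investigator will determine the severity of the AE based on the following definitions".

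On that fallback scale:

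- Grade 2 is interference with routine activity that responds to symptomatic treatment or rest. It adds a drug clause: "The AE may require reducing the dose, but not discontinuing administration of the study drug".
- Grade 3 has a clinical part, "The AE significantly limits the patient's ability to perform routine activities despite symptomatic therapy", and a second, cumulative part: "In addition, the AE leads to discontinuing administration or reducing the dose of the study drug".
- Grade 4 reads: "The AE requires discontinuing administration of the study drug. The patient is at immediate risk of death".
- Grade 5 is a death resulting from a condition brought about by giving the study drug.

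Section 7.1.3 has AEs reported in both treatment groups. Section 8.6 says that AE rates "categorized by toxicity grades (severity) will be described for each treatment arm and be compared between two arms". Section 6.1.1 lists severity, relatedness and action taken with the study drug as separate items for each AE.

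**The concern.** A severity grade should describe how ill the patient is. Here, part of the grade describes what was done with the drug (grades 3 and 4) or what caused the event (grade 5). Two patients with the same clinical event can then receive different grades because one was taking EACA and the other was not, or because one investigator changed the dose and another did not.

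The trial is open label, one arm takes tablets that can be reduced or stopped, and the other receives platelet transfusions. A scale tied to drug action therefore does not work the same way in both arms. Safety is a listed secondary endpoint, and section 8.6 tests AEs by grade between arms. The grade is assigned by the investigator when the event occurs, so a later analysis plan cannot recover a clinical severity that was never recorded apart from the drug action.

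**Working it through.** No figure in the protocol bears on this point and no arithmetic applies. The check is to apply the definitions as written.

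**Step 1: what study drug means.** Section 5.4 glosses the term as EACA in its clause on treatment interruption. Section 6.5.3.1 calls EACA the investigational drug product. Section 8.2 defines the safety population by a dose of EACA where section 8.6 speaks of a dose of study drug. Section 7.1.6 foresees patients who received no study drug. The natural reading is that study drug means EACA.

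**Step 2: one clinical event, three patients.** Take an event not defined in CTCAE v4.0 that severely limits routine activity despite symptomatic therapy, without immediate risk of death.

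| Patient | Grade 3, clinical part | Grade 3, drug part | Grade 2 | Result |
|---|---|---|---|---|
| EACA arm, EACA reduced or stopped because of the event | met | met | not met | grade 3 |
| EACA arm, EACA continued unchanged | met | not met | not met: event does not respond to therapy or rest | no grade fits |
| Platelet arm, no EACA | met | cannot be met | not met, same reason | no grade fits |

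The clinical state is the same in all three rows, and only the first yields a grade.

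**Step 3: grade 4.** The definition is two sentences, one on discontinuation and one on immediate risk of death. If both are required, a platelet-arm patient at immediate risk of death fails it. If the second sentence is taken as the criterion and the first as its usual consequence, that patient is grade 4. The text does not settle which applies.

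**Step 4: grade 5.** Death is a severity level, but the definition admits only deaths caused by the study drug. A platelet-arm death cannot meet it if study drug means EACA, and an EACA-arm death meets it only if judged drug-induced. Relatedness has its own scale in section 7.1.6.

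**Step 5: the lower grades.** Grade 2 excludes discontinuation. An event that is clinically moderate but leads to stopping EACA is therefore not grade 2, and it lacks the clinical part of grade 3. The drug clauses leave gaps below grade 3 as well.

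**Step 6: where the grades are used.** Section 8.6 compares frequencies by grade between arms. For events on the fallback scale, and with study drug meaning EACA, grade 3 can be recorded only in the EACA arm. Where platelet-arm patients are included in that comparison, the distortion at grade 3 counts against EACA.

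**The case against.** Several points on the other side are sound.

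- **The term is used loosely.** Section 5.4 lists events on either arm among the reasons to stop study drug. Section 8.6 compares two arms among patients with at least one dose of study drug. On the strict reading, platelet-only patients would fall outside that set and there would be no control distribution to distort. On the loose reading, control patients do have a treatment that can be stopped. Section 8.5.3 compares safety in the ITT population but does not mention grades. A reader might infer that a platelet-arm event can never be grade 3 or 4. The documents do not support so absolute a statement: it depends on one reading of the term and, for grade 4, on treating both sentences as required.
- **Attribution is not the only route to a drug change.** Section 6.3.3 covers patients "who experience grade ≥ 2 toxicity attributable to EACA, will hold the study drug until resolution of the adverse event", and a reader might infer that grade 3 simply follows the investigator's attribution to EACA. But section 5.4 allows EACA to be stopped for reasons with no attribution test, including thrombosis, DIC and the investigator's judgement. An unattributed severe event that leads to stopping can meet grade 3.
- **The circularity is partial.** A reader might say that grade and drug action define each other. The trigger in section 6.3.3 is grade 2 or higher, and grade 2 can be assigned with no drug action. Only the grade 3 label depends on what follows.
- **The reach is limited.** CTCAE v4.0 is the main scale, bleeding is graded by WHO, and section 7.2.1 captures life-threatening events and hospitalisations as SAEs without reference to drug action. A count of misgraded events would need rates that the protocol does not give, so none is offered here.

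These points narrow the concern but do not remove it. On either meaning of study drug, grade 3 still depends on a treatment action and not on clinical state alone. The middle row of the table above, within the EACA arm, does not depend on how the term is read for the platelet arm.

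**Conclusion.** The concern holds in a limited form. For AEs not defined in CTCAE v4.0, section 7.1.5 mixes drug action into severity, explicitly at grade 3 and less explicitly at grade 4, and mixes causality into grade 5. Severe events with EACA unchanged have no fitting grade. The same is true of severe events in platelet-arm patients if study drug means EACA, which is the better-supported reading.

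The by-grade comparison in section 8.6 is distorted for this subset. The protocol does not give its size. It is probably small, because CTCAE covers the AEs it defines and only the remainder reaches the fallback scale. If the loose meaning of study drug is intended, the arm imbalance weakens and its direction is no longer clear, but the dependence on treatment action remains. CTCAE-graded AEs, WHO-graded bleeding, the primary endpoint and the interim analyses are unaffected. This is a wording correction worth making, not a threat to the trial's main conclusion.

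**What to change.** In section 7.1.5:

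1. Remove the clauses on reducing or discontinuing the study drug from the severity definitions at every grade where they appear.
2. Remove the drug-causality wording from grade 5, so that it records death due to the AE.
3. Grade on the clinical criteria already in the section: whether routine activity is affected, whether the event responds to or persists despite symptomatic therapy, immediate risk of death, and death.
4. Keep action taken with the study drug and relatedness as the separate items listed in section 6.1.1.

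The same edit should say whether study drug in sections 5.4, 7.1.5 and 8.6 means EACA only or the assigned treatment in either arm.

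The cost is a few deleted clauses and one clarifying sentence. No new data are needed and nothing is lost, because action taken is already collected. Fallback-scale events already recorded would need their grade checked against the clinical description. The edit leaves the dose rules in section 6.3.3 and the withdrawal rules in section 5.4 as written.

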7.1.6 Causality

The investigator's assessment of causality must be provided for all AEs (serious and non-serious). An investigator's causality assessment is the determination of whether exists a reasonable possibility that the investigational product caused or contributed to the AE. In addition, if the investigator determines an SAE is associated with study procedures, the investigator must record this causal relationship in the source documents and on the SAE form and report such an assessment in accordance with the SAE reporting requirements. The investigator will use medical consideration and use the following categories of causality to determine the relatedness of an AE with the study drug based on the following definitions. Not all criteria in each category of relatedness must be present.

- Definitely Not Related (not drug related): The patient did not receive study drug, OR the temporal sequence of the AE onset relative to the administration of the study drug is not reasonable, OR there is another obvious cause of the AE
- Probably Not Related (not drug related): there is evidence of exposure to study drug, there is another more likely cause of the AE, dechallenge (if performed) is negative or ambiguous, rechallenge (if performed) is negative or ambiguous
- Possibly Related (drug related): there is evidence of exposure to study drug, the temporal sequence of the AE onset relative to administration of the study drug is reasonable, the AE could have been due to another equally likely cause, dechallenge (if performed) is positive
- Probably Related (drug related): there is evidence of exposure to study drug, the temporal sequence of the AE onset relative to administration of the study drug is reasonable, the AE is more likely explained by the study drug than by another cause
- Definitely Related (drug related): there is evidence of exposure to study drug, the temporal sequence of the AE onset relative to administration of the study drug is reasonable, dechallenge is positive, rechallenge (if feasible) is positive, the AE shows a pattern consistent with previous knowledge of the test drug or a test drug class

7.1.7 Expectedness

The expectedness of an SAE is assessed by the Investigator in the overall classification of SAEs for regulatory reportability. The EACA Investigator's Brochure will be used as the reference for determination of expectedness and risk assessment.

7.2 Serious Adverse Events

The definitions and reporting requirements of ICH Guidelines for Clinical Safety Data Management, Definitions and Standards for Expedited Reporting, Topic E2A, will be adhered to.

7.2.1 Serious Adverse Event Definition

An AE is considered an SAE if at least one of the following conditions applies:

- Death: An AE that results in death is any patient death within 30 days of the last dose of study drug administration. The cause of death or AE that resulted in a fatal outcome is the SAE
- Life-threatening AE: An AE that places the patient, in the view of the investigator or the sponsor, at immediate risk of death from the event as it occurred (i.e., this does not include an event that had it occurred in a more severe form might have caused death)

- Results in a persistent or significant incapacity or substantial disruption of the ability to conduct normal life functions: Any substantial disruption of a person's ability to conduct normal life functions
- Inpatient hospitalization or prolongation of existing hospitalization: Hospitalization refers to admission of a patient into a hospital for any length of time
- A congenital anomaly/birth defect: A fixed, permanent impairment established at or before birth
- Cancer: Occurrence or diagnosis of a new cancer during the study is considered an SAE. A new cancer is a cancer that is histopathologically different than the cancer under study in the trial (ie, does not include metastatic or progressive disease)
- Overdose: Occurrences of overdose must be reported as an SAE
- Important medical event: Medical and scientific judgment should be exercised in determining whether an event is an important medical event. An important medical event may not result in death, be life-threatening, or require hospitalization. However, if it is determined that the event may jeopardize the patient and/or may require intervention to prevent one of the other outcomes listed in the definition above, the important medical events should be reported as serious. Examples of such events are intensive treatment in an emergency room or at home for allergic bronchospasm, blood dyscrasias, or convulsions that do not result in hospitalization; or the development of drug dependency or drug abuse.

Adverse events (reported from clinical studies) that require hospitalization or prolongation of hospitalization are considered serious. Any initial admission (even if less than 24 hours) to a health care facility meets these criteria. Adverse events that require emergency room care that do not result in hospital admission are not SAEs unless assessed by the investigator to be an important medical event. Hospitalization does not include the following: Hospice facilities, Respite care, skilled nursing facilities, Nursing home, Routine emergency room admissions, and same day surgeries (as outpatient/same day/ambulatory procedure)

Hospitalization or prolongation of hospitalization in the absence of a precipitating AE is not in itself an SAE. Examples include: Social admission (eg, patient has no place to sleep), Protocol-specified admission during a clinical study (eg, for a procedure required by the study protocol), Optional admission not associated with a precipitating AE (eg, for elective cosmetic surgery that was planned prior to study enrollment [appropriate documentation is required for these cases]), Hospitalization or prolongation of hospitalization for scheduled therapy of target malignancy of the study is not considered an SAE

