5.4 Withdrawal Criteria

- Patients will be discontinued from further study drug administration if any of the following occur:
Intolerable toxicity as determined by the Investigator
- Grade 4 bleeding on either arm of this study
- Development on trial of a deep venous thrombosis, pulmonary embolism or cerebrovascular event on either arm of this study
- Grade ≥ 2 CPK elevation on the EACA arm
- Grade ≥ 3 myalgia on the EACA arm
- Development on trial of disseminated intravascular coagulation (DIC)
- Development on trial of a condition that requires anticoagulation
- A treatment interruption for study-drug (EACA) related non-hematologic toxicities lasting longer than 28 days
- Significant deviation from the protocol or eligibility criteria
- Noncompliance with study or follow-up procedures
- Pregnancy
- Patient withdrawal of consent and decision to discontinue participation
- Termination of the trial
- Any other reason that, in the opinion of the Investigator, would justify removal of the patient from the study

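### The 7.2.1 death criterion and the 7.1.5 fallback grades hang on study drug rather than assigned treatment, so SAE and grade capture can differ between arms by definition, and 7.1.6 has no relatedness category for non-serious platelet transfusion reactions

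*Protocol*

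**What the plan says.** Section 7.2.1 opens its list of SAE criteria with death: "An AE that results in death is any patient death within 30 days of the last dose of study drug administration". It adds that the cause of death, or the AE with the fatal outcome, is the SAE.

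Section 5.4 shows what study drug usually means here: "A treatment interruption for study-drug (EACA) related non-hematologic toxicities lasting longer than 28 days". Sections 6.3.3 and 6.5.3 also use the term for EACA tablets.

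Section 7.1.4 sets the recording period for AEs and SAEs in all enrolled patients by a different anchor, "concluding 30 days following the last dose of the assigned study treatment", or the decision to discontinue if that is later. Section 7.2.3 (SAE monitoring) and the survival follow-up in 5.1 use the same anchor.

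Section 7.1.5 grades severity by CTCAE and gives fallback definitions for AEs that CTCAE does not define. Fallback grade 3 includes stopping or reducing study drug, grade 4 requires stopping it, and grade 5 reads: "The patient dies as a direct result of the complication or condition induced by administration of the study drug".

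Section 7.1.6 rates causality. Its lowest category begins: "Definitely Not Related (not drug related): The patient did not receive study drug, OR the temporal sequence of the AE onset". The first drug-related category begins "Possibly Related (drug related): there is evidence of exposure to study drug", and the two above it also list exposure. The section also says: "Not all criteria in each category of relatedness must be present".

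Safety in each arm is a secondary endpoint (3.3). It is compared by Fisher's exact test on the ITT population (8.5.3), and AE incidence and toxicity by grade are compared between the arms (8.6).

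**The concern.** The comparator is itself an assigned treatment with its own reactions, yet three definitions that shape safety data at capture are written around EACA. A between-arm safety comparison needs the same event to be classified in the same way in both arms. If a death is automatically serious in one arm and serious only on a further judgement in the other, a difference in SAE counts partly reflects the definition. If a severe event outside CTCAE can reach a fallback grade only through action on EACA, the grade distribution has the same weakness. If causality is never asked about platelets, the trial cannot describe how often non-serious transfusion reactions were judged related to the transfusion, in a study whose rationale is an alternative to transfusion.

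**Working it through.** There is no stated figure to reproduce. The check sets the definitions side by side.

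**1. Death criterion against the recording window**

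| Section | Anchor | Can a platelet-arm patient have it? |
|---|---|---|
| 7.2.1 death criterion | last dose of study drug | No, if study drug is EACA |
| 7.1.4 AE and SAE recording | last assigned study treatment, or decision to discontinue, whichever is later | Yes |
| 7.2.3 SAE monitoring | same as 7.1.4 | Yes |
| 5.1 survival follow-up | last assigned study treatment, or decision to discontinue, whichever is later | Yes |

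An EACA-arm death within 30 days of the last dose is an SAE whatever its cause. The same death in the platelet arm must qualify through another criterion, such as a life-threatening event, hospitalization or an important medical event. Those depend on the circumstances and on judgement. For example, 7.2.1 does not count hospice, nursing home or skilled nursing facility care as hospitalization.

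The two windows also differ within the EACA arm. Section 5.4 discontinues a patient after a toxicity-related interruption of more than 28 days. If the decision to discontinue comes 28 days after the last dose, the 7.1.4 window closes 28 + 30 = 58 days after that dose, while the 7.2.1 window closes at 30 days.

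**2. Fallback grades**

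| Fallback grade | Condition on study drug | Literal reach in the platelet arm |
|---|---|---|
| 3 | stopped or reduced | cannot be met |
| 4 | must be stopped | cannot be met |
| 5 | death induced by it | cannot be met |

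This applies only to AEs not defined in CTCAE. Those grades enter the comparison of toxicity by grade in 8.6.

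**3. Causality**

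In 7.1.6 the conditions of the lowest category are joined by OR, so not having received study drug is sufficient for it. No category asks about the platelet transfusion. The separate causal record for study procedures covers SAEs only, and 7.2.2 asks for the relationship of an SAE to the study drug. A non-serious platelet transfusion reaction is therefore never rated against the transfusion. Under 5.1 and 7.1.4, non-serious AEs still ongoing after 30 days are followed only if possibly related to study drug, so the rating also decides what is followed.

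**4. Size, as an illustration**

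- Platelet arm: 50 of 100 patients (8.4).
- Assumed share dying within the window, 10% to 30%: 0.10 × 50 = 5 and 0.30 × 50 = 15 deaths.
- Upper end, if deaths were as frequent as in the preliminary EACA cohort (Table 2: 25/44 = 57%): 0.57 × 50 = 28.5, using the unrounded 25/44 gives 28.4, or about 28 deaths.

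These are deaths whose SAE status would rest on another criterion. They are not unrecorded deaths. The 57% comes from an uncontrolled EACA cohort, 71% relapsed or refractory, and is not an estimate for the platelet arm.

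**The case against.** The best defence is that other sections cover both arms. Section 7.1.3 reports all AEs regardless of treatment group, 7.1.4 and 7.2.3 use arm-neutral windows, 5.1 tracks survival in both arms, and 7.2 commits in general terms to the ICH E2A definitions. This stands as far as recording goes. A reader might infer that platelet-arm deaths are never SAEs or go unreported; the documents do not support that. Deaths are recorded in both arms, many would meet another SAE criterion, and death within 30 days of ending treatment could be derived later for either arm. What remains is that 7.2.1 gives its own specific definition, which disagrees with the neighbouring sections.

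A reader might also infer that every platelet transfusion reaction must be coded as definitely unrelated and is thereby hidden. That goes too far. The scale measures relatedness to study drug, so a not-drug-related answer is formally correct for a patient never given EACA. The criteria are not all mandatory, infusion reactions are documented (6.3.1.2), SAEs from study procedures have their own causal record, and 7.4 treats consequences of standard-of-care procedures as related when judging unanticipated problems. The gap is confined to relatedness of non-serious reactions.

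A third tempting inference is that the planned comparison is skewed against EACA. No comparison by relatedness or by the death criterion is stated, since 8.6 uses AE incidence and grade. Only the fallback grades reach that analysis directly. SAE counts would matter if tabulated by arm.

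Finally, study drug is used loosely: 5.4 applies discontinuation of study drug to events on either arm, and 8.6 makes patients with a dose of study drug evaluable and then compares two arms. The term is therefore ambiguous. That weakens any claim of certainty, but two readings that give different SAE counts are a reason to settle the wording.

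**Conclusion.** The point holds as an inconsistency in definitions that can make SAE and grade capture differ between arms. The 7.2.1 death window conflicts with 5.1, 7.1.4 and 7.2.3. The 7.1.5 fallback grades 3 to 5 cannot literally be met in the platelet arm. Section 7.1.6 leaves non-serious platelet transfusion reactions without a relatedness category.

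This rests on reading study drug as EACA, which most of the protocol supports but does not apply uniformly. Up to half the trial, 50 of 100 patients, is exposed to the asymmetry. The 5 to 15 deaths are an illustration under an assumed 10% to 30%, and the documents give no platelet-arm death rate. Neither the size nor the direction of any effect on the planned safety comparison can be derived from the documents. The requirement in 8.2 of an EACA dose for entry to the safety population is a separate matter, and correcting it would not repair seriousness, grade or relatedness as captured. The change is worth making because it is specific and cheap.

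**What to change.** - **7.2.1:** anchor the death criterion on the 7.1.4 window in both arms, that is, 30 days after the last assigned study treatment or the decision to discontinue, whichever is later.
- **7.1.5:** define the fallback grades by severity alone, without reference to action on study drug, and define grade 5 as death due to the AE.
- **7.1.6:** record causality to EACA and causality to platelet transfusion as two separate fields in both arms. Keep the EACA field for FDA expedited reporting.

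Two fields are better than one field for assigned treatment because 6.3.1.3 gives therapeutic platelets in both arms. With a single field, the same transfusion reaction could be related in the platelet arm and unrelated in the EACA arm.

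The cost is amendment wording, one extra CRF field and a few more SAE forms in the platelet arm. The CRF itself is not shown, so the single extra field is an assumption.
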